4.5.3 Additional data

We will gather additional consistent data, which will be available for future observation and comparison.

- Using a technical device (beacons), we will record the precise indoor location of the resident during observation. Location will be correlated to activities.
- Using software and IT logs, we will collect the number of clicks, mouse distances, and EMR usage during observation.
- Using certified tests, we will assess dactylography skills of residents and correlate them with medical record activities.
- Using focus groups, we will correlate the results of observations with a qualitative analysis described in section 4.6.

4.6 Focus group

The focus group is a qualitative research method using group interviews. Focus group participants are invited to discuss topics proposed by the researcher, usually in a semi-structured way with a set of predefined open-ended questions. Focus groups rely on group dynamics to gather and explore participants' perspectives. While the researcher acts as a moderator, group discussions deepen and enrich the original perspective of each participant. (Britten *et al.*, 1995; Kuper *et al.*, 2008; Moreau *et al.*, 2004)

All observed residents will be invited to focus groups at the end of the observation period. We will organize 4 to 6 sessions, depending on the number of participants (about 8 per group). An experienced moderator will guide the sessions, which will be audio recorded for further transcription. Nonverbal instances will be observed during the discussions and gathered by a research assistant. Focus group discussions will be transcribed verbatim and thereafter analyzed. Inductive analysis will be performed by two independent researchers and agreement between researchers will be looked after. This process will yield a series of critical themes representing the key results of this part of the project.

The aim of the qualitative analysis is to gain insight of what lies behind the numerical results and to understand which behaviors, beliefs or situations could explain these results. In view of the objectives of the study, the moderator will explore following questions:

- Having seen the raw results and your experience, how do you appreciate the primary and the four secondary outcomes results? Is it not enough, right amount, or too much?
- What are the causes of mismatch, interruption or perturbation?
- What are the needs for professional satisfaction? How can we meet your expectations?

4.7 Statistical methods

A first analysis will be conducted to produce the descriptive results for this study. Descriptive results for the participant's characteristics will be expressed as average \pm standard deviation or as number of participants and (percentage) according to the variable of interest. We will use a mixed model using the participant as a cluster to compute means and corresponding 95% confidence intervals for the times dedicated to each activity. The percentage of a participant's shift time devoted to each activity will be computed by dividing the time for that activity by the total shift duration.

The second analysis will compare the first and second surveys. The analysis will be conducted using mixed models using the participant as a cluster (random part) and adjusting for the participant's characteristics (fixed part). Results of the multivariate analysis will be presented as multivariable adjusted average and corresponding 95% confidence interval. One-sided tests will be used and statistical significance will be considered for p<0.05.

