4 METHODS

4.1 Study outcomes

4.1.1 **Primary outcome**

The primary outcome will be the **time spent for administrative tasks**, defined as the sum of the four following activities (see **appendix table 1** for all definitions):

Patient administrative tasks	(defined as administrative tasks for the patient: booking appointments, writing the voucher for radiography or specialized consultation, and adding laboratory tests)
Non-patient administrative tasks	(defined as an activity unrelated to the patient, directly or indirectly, e.g., answering professional e-mails)
Discharge summary redaction	(defined as any activity related to writing hospitalization reports: brief report and discharge letter. Includes revision of reports)
Looking for information	(defined as looking in the paper record, EMR, computer archives, or other medical record. Excludes admission activity. Excludes literature reviewing)

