4.5.1 Observation of activities during a shift

Definition of a shift

The official dayshift begins at 08:00 and ends at 18:00. The evening shift begins at 16:30 and ends at 23:00. Starting in 2017, following legal regulation changes, the official day shift ends at 18:24 and the evening shift ends at 24:00. However, observation will start when residents arrive at their workplace on the ward - but not earlier than 30 minutes before the official time - and stop when they definitely leave the workplace at the end of the day, no matter how early or late. Night shifts and weekends will not be observed.

Observation and randomisation

We will observe all eligible residents twice, on two different days, for the duration of a whole shift. The period of observation will last 2 months. We will randomize the days of observation with a stratification for day and evening shifts and for days of the week. After randomisation, observation days are attributed to observers, based on their availability but blindly to the observed residents. The observer will get contextual information about the intern (place of work, patients in charge, rooms in charge, supervisor) on the night before. On the assigned day of observation, he will wait for the intern at his regular workplace, 30 minutes before the official beginning of the shift. If resident-observer contact is not made 15 minutes before the official beginning of the shift, the observer will call the intern to make first contact. During dayshifts, a second observer will relay the first after 6 hours of observation.

Observers will use the dedicated tablet application developed in our department as described in Wenger *et al.* (2017).

Selection and training of observers

We will recruit and pre-select candidates with personal interest in internal medicine, ongoing or completed undergraduate medical education, fluent French speaking and understanding, and easiness with IT devices.

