4.8 Methods of minimizing bias

Based on literature and our previous study, we identified the following potential biases.

- (1) The observation bias (Hawthorne's effect) cannot be avoided. We will recruit observers among medical students, acting like other students in our ward. We will not communicate the day of observation to the resident. No contact between the observer and the resident will be allowed with the following exception: observer may occasionally ask the resident for precision about the current activity, if in any doubt about what he is doing.
- (2) Observers might misinterpret the current activity of a resident, occasionally or systematically. We will train observers with a standard video and blank observations. During a subsequent meeting, the observers will share their experiences and each dubious interpretation of activities will be answered and protocoled. Finally, we will assess and publish reproducibility during the practice session.
- (3) The workload of a resident highly depends on the number of patients in his charge, day of observation, and backlog of administrative task. To minimize this, we will randomize the shifts to be observed, with stratification to the day of the week.
- (4) We are already aware of the results of the "before" observation. We might therefore misguide observers towards the expected outcomes. During the study period, the observers and the investigator will be blinded to the results. A single designated investigator will check and process collected data to avoid IT issue.
- (5) Residents may misinterpret the present study as a way for the management to check their duty hours and then retaliate, despite the assurance of anonymization. This misunderstanding could lead to major modifications in the behaviour of some residents but it will not be possible to assess in what way: would they stay later on purpose or, on the contrary, end at the official time? We will mitigate this risk by designing an external and neutral person as "ombudsman".
- (6) The design of our study is based on a consistent observation on both before and after groups. Nevertheless, we considered the implemented reforms as interventions and chose outcomes described in the present protocol afterwards. We may thus have eliminated unfavourable outcomes.

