8 BUDGET ESTIMATION

Table 5 presents the forecasted expenses and incomes of the study. The data of the 2015 baseline study are available without additional charge.

					Inco	mes				
Item	Amount and rate	Exp	Expenses		Expenses				SSMIG- foundation	
				fu	nding	tou	ndation			
Cost of observer labour: Day hours 6 am to 8 pm) Special hours (8 pm to 6 am)	24 CHF / hour 31 CHF / hour									
Half-day training Half-day blank observations	4 hours 8 hours									
Number of observers	5 to 8									
One day shift One evening shift	11 to 15 hours 4 h and 3 to 5 special h									
Number of observed shifts	70 (2 x 35)									
Total day hours	50 * (11 to 15) + 20 * (4) + 12 * (5 to 8) = 690 to 926 hours	CHF	22'220			CHF	22'220			
Total special hours	20 * (3 to 5) = 60 to 100 hours	CHF	5'020			CHF	5'020			
Project manager	3 months, part time	CHF	10'000	CHF	7'000	CHF	3'000			
Dactylography skill test	35 * 30 CHF	CHF	1'050			CHF	1'050			
Recording device (tablet)	4 * 400 CHF	CHF	1'600			CHF	1'600			
Preparation of tablet application		CHF	5'000	CHF	5'000					
Devices for localization (beacons)	50 * 50 CHF + 500 CHF	CHF	3'000			CHF	3'000			
Focus group manager		CHF	12'000	CHF	7'000	CHF	5'000			
Statistician fee	50 * 120 CHF	CHF	6'000	CHF	6'000					
Publication fee provision		CHF	2'000			CHF	2'000			
Communication, transport, posters		CHF	1'000			CHF	1'000			
Overhead	(15%)	CHF	9'110	CHF	3'000	CHF	6'110			
Total		CHF	78'000	CHF	28'000	CHF	50'000			

Table 5. Estimation of expenses and incomes for the study.

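### The before-after model leaves out shift type and weekday, the factors that stratify the observation days; the precision cost is modest and any bias depends on an unstated 2015 shift mix

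*Protocol*

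**What the plan says.** - **Design.** Section 4.5.1: "We will randomize the days of observation with a stratification for day and evening shifts and for days of the week".
- **Reason given.** Section 4.8, item 3: "The workload of a resident highly depends on the number of patients in his charge, day of observation, and backlog of administrative task". The remedy offered there is at the design stage: "we will randomize the shifts to be observed, with stratification to the day of the week".
- **Comparison model.** Section 4.7: "mixed models using the participant as a cluster (random part) and adjusting for the participant's characteristics (fixed part". Table 2 (section 4.5.2) lists age, sex, country of diploma, training, distance to home and number of patients in charge. Shift type and weekday are not on the list, and no other section adds them to the model.
- **Outcome.** Section 4.1.1: time on administrative tasks, "defined as the sum of the four following activities". It is a total, not a rate. Percentages of shift time appear only in the descriptive analysis.
- **Shift lengths.** Section 4.5.1: "The official dayshift begins at 08:00 and ends at 18:00. The evening shift begins at 16:30 and ends at 23:00"; from 2017, "the official day shift ends at 18:24 and the evening shift ends at 24:00".
- **Planned mix.** Table 5 (section 8) costs the day hours as "50 * (11 to 15) + 20 * (4) + 12 * (5 to 8", that is, 50 day shifts and 20 evening shifts.
- **Population.** The synopsis describes following residents on a randomised day shift, and the sample size (synopsis and section 4.7.2) uses 92 minutes per day shift. Sections 4.5.1 and 8 include evening shifts.

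**The concern.** When days are sampled within strata, the analysis should normally carry those strata. Here the plan controls for shift type and weekday when choosing the 2018 days, then states a model that names neither.

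Two things follow. First, if day and evening shifts have different mean administrative time, the difference goes into the residual and the before-after contrast loses precision. Second, survey period is not randomised. Stratifying the 2018 days cannot balance them against days observed in 2015, and section 7 requires only that the calendar period match. If the evening share or weekday mix differs between surveys, the difference shows up as a before-after change. A larger evening share in 2018 would lower the pooled mean, which is the direction the one-sided test looks for; a smaller share would hide a true reduction.

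The conflicting wording on day shifts makes this harder to settle, because the protocol does not say whether the primary comparison pools the two shift types.

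**Working it through.** **Inputs from the protocol.** Day mean 92 min; spread 36 min (called a standard error, used here as an SD, the only reading that gives a detectable effect near the stated one); one-sided 0.05; power 80%; 36 doctors or 66 observations in 2015; up to 70 observations in 2018; evening share p = 20/70 = 0.286; the official shift lengths above.

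**Assumptions, not in the protocol.** The evening mean. The main case scales it with official length; larger gaps are shown for range. The 36 min is taken as the SD within shift type.

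**The plan's own figure.** Detectable effect = (1.645 + 0.842) x SD x sqrt(1/n1 + 1/n2).
- 36 per survey: 2.486 x 36 x sqrt(2/36) = 21.1 min, close to the stated 20 but not equal.
- 66 per survey: 15.6 min. For 66 against 70 shifts: 15.4 min.

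The mismatch with 20 min is a separate matter and does not affect the comparison below.

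**Effect of leaving out shift type.** Gap d = 92 x (1 - evening/day ratio). Added variance = p(1-p)d², with p(1-p) = 0.204, set against 36² = 1296. False change per 10-point difference in evening share = 0.10 x d.

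| Evening/day ratio | Gap d (min) | Added variance | Rise in variance | Pooled SD | Detectable effect, 66 vs 70 | False change per 10 points |
|---|---|---|---|---|---|---|
| 7.5/10.4 (from 2017) | 25.7 | 134 | 10% | 37.8 | 16.1 min | 2.6 min |
| 6.5/10 (2015) | 32.2 | 212 | 16% | 38.8 | 16.6 min | 3.2 min |
| 0.50 | 46 | 432 | 33% | 41.6 | 17.7 min | 4.6 min |
| 0.25 | 69 | 972 | 75% | 47.6 | 20.3 min | 6.9 min |

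The detectable effect grows by the square root of the variance ratio: sqrt(1.104) = 1.05 and sqrt(1.163) = 1.08 in the two length-proportional cases.

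**Simulation check.** Random-intercept data, 66 against 70 shifts, two per resident, total within-type SD 36, assumed between-resident SD 18, gap 32.2 min, 3000 data sets per case:
- Equal evening share: standard error 7.3 min without shift type and 6.9 with it; power for a 20-min reduction 88% and 91%.
- Evening share 9 to 10 points higher in 2018, no true effect: one-sided rejection rate 0.09-0.10 without shift type, 0.05 with it.
- About 19 points higher: 0.21 without, 0.05 with.

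**Weekday.** The protocol gives no means by weekday, so no size can be attached to that part.

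**The case against.** **Covariate lists are often left to an SAP, and section 4.7 does not say that nothing else may enter.** That is fair as far as it goes: the protocol does not forbid the strata. But it does not defer the model either. It states a fixed part, and the design factors are not in it.

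**A reader might infer that the comparison is biased.** The documents do not support that. Bias needs a different mix in the two surveys, and the 2015 evening share is not stated. The baseline average is 697 h / 66 = 10.6 h per shift. With 12 h day and 7 h evening shifts (illustrative values), the implied share is (12 - 10.56)/(12 - 7) = 29%, the same as planned for 2018. With 11 h day shifts it would be 11%, and with 13 h 41%. The average therefore neither shows an imbalance nor rules one out.

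**A reader might infer a severe loss of power.** That needs an evening mean far below what official length suggests. In the length-proportional cases the detectable effect for 66 against 70 shifts stays at 16-17 min, under the 20-min target. And if the 36 min already describes day and evening shifts together, it contains the extra variance. Nothing is then inflated; instead, a shift-type term would bring the SD down to about 33-34 min.

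**A reader might infer that day shifts alone must be the primary comparison,** since the 92 min refers to them. The protocol conflicts with itself here and does not settle it. If the primary comparison is day-only, the day/evening argument disappears and only weekday remains.

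**Part of the workload is already handled.** Number of patients in charge, the first workload driver named in section 4.8, is in Table 2 and so in the planned adjustment. It may absorb some of the day/evening difference but does not replace shift type.

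**Conclusion.** The point holds in a limited form. The comparison model as written does not include the two factors by which the days are stratified, although the outcome is a total and the shift types differ in length by design.

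If administrative time is proportional to official length and 36 min is the within-type SD, leaving out shift type raises the variance by about 10-16% and the detectable effect by about 5-8%. That is a moderate loss. The stronger reason to act is protection against unequal mix: about 2.6-3.2 min of false change per 10 points of evening share, or 13-16% of the 20-min target, and more if the gap is larger. This second effect is conditional on an imbalance that the protocol neither reports nor excludes. The conflict over which shifts the primary comparison covers is there in the text and needs no assumption.

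**What to change.** In section 4.7, specify the comparison along these lines: *mixed model for administrative minutes per shift, with survey, shift type (day or evening), weekday and the planned resident characteristics (including number of patients in charge) as additive fixed effects, and a random intercept for resident.*

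Do not adjust for the actual duration of the shift. It is a secondary outcome that the reforms may change.

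State which shifts the primary comparison covers, and reconcile the day-shift wording in the synopsis and section 4.7.2 with the evening shifts in sections 4.5.1 and 8.

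Report the survey-by-shift-type interaction and the day-shift-only contrast as sensitivity analyses. They are useful because the official lengths rose unequally between surveys (day by 24 min, evening by 60 min).

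**Cost.** About five degrees of freedom: one for shift type and four for Monday to Friday, as weekends are not observed. No new data collection is foreseen: shift type and weekday are design variables in 2018, and section 8 says the 2015 data are available. Making the day-shift contrast primary would cost more. With SD 36 and the same evening share assumed in 2015 (about 47 of 66 day shifts), the detectable effect is 2.486 x 36 x sqrt(1/50 + 1/47) = 18.2 min against 15.4 min for all shifts, about 18% worse. That is why it is proposed here only as a sensitivity analysis.

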4.7.1 Hypothesis

The null hypothesis is that no intervention changed any outcome. The alternative hypothesis is that interventions reduced the time spent for administrative tasks. Secondly, it reduced task-switching and, on the contrary, increased time with patients.

4.7.2 Sample size

Based on four previous and similar studies (Ammenwerth *et al.*, 2009; Block *et al.*, 2013; Fletcher *et al.*, 2012; Westbrook *et al.*, 2008) that studied between 12 to 29 doctors, we have chosen a convenient sample of 35 residents. Each resident will be observed during two shifts.

Using an average time spent on administrative tasks (92 minutes per dayshift), a standard error of 36 minutes, a one-sided test, a significance of 0.05, a power or 80%, and supposing equally sized samples (either 36 doctors or 66 observations as in our 2015 baseline study), then the minimum detectable effect size will be 20 minutes, which corresponds to a reduction of just over 20% of the time dedicated to administrative tasks. Calculations were performed using the **power twomeans** command of stata and recalculating the standard deviation from the standard error. The full code can be provided upon request.

Depending on the final number of residents consenting to participate, we will end up with a sample size of up until 70 observations.

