Study Title:	Impact of Structural and Organizational Reforms on Residents' Daily Work.
Study ID:	MED2DAY
Version and Date:	V1.0, 26.02.2018
Trial registration:	Intended registry: ISRCTN
Background and Rationale:	Because of an increasing number of complex polymorbid patients, a heavier administrative burden, and the evolution of young residents' expectations, organization of work in internal medicine wards is of outmost importance. In a 2015 study, we showed that residents spent 1.5 hours on administrative tasks and 1.7 hours with patients per day. In addition, residents switched activity on average 15 times per hour. This study motivated major reforms: task delegation to non-medical professionals, reorganization of the workday's schedule, and implementation of an early morning inter-professional decision meeting. An associated reduction in administrative and working hours and increased time with patients could greatly improve job satisfaction and attractiveness for internal medicine.
Objectives:	We aim to quantify the impact of the organizational and structural reforms implemented in our department between 2016 and 2017 on: 1) residents' administrative workload; 2) continuity and adequacy of work; 3) duration of shifts, and 4) time spent with patients.
Outcomes:	 Time spent for administrative tasks (primary outcome) Amount of task switching per hour. Mismatch between observed activities compared to the departmental work schedule. Effective duration of observed shifts. Time spent in presence of a patient.
Study design:	Time and motion study with a before and after comparison.
Inclusion / Exclusion criteria:	Inclusion criteria: all residents registered in the internal medicine department during the study, having graduated from a medical school, and with informed consent. Exclusion criteria: none.
Measurements and procedures:	Trained observers will follow residents during a randomized dayshift and record activities and context, using a dedicated tablet application. Additionally, residents will be included in focus group.
Number of Participants:	35 participants, observed twice (70 observations). Based on our previous study, this number will be sufficient and cost-effective to show a significant reduction of 20 % of administrative tasks.
Study Duration:	4 months
Study Schedule:	May to August 2018

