Investigators:	[name], [name], [name], [name], [name], [name], [name], [name], [name], [name], [name]
Study Centre:	Lausanne University Hospital, Switzerland (CHUV)
Statistical Considerations:	Using an average time spent on administrative tasks (92 minutes per dayshift), a standard error of 36 minutes, a one-sided test, a significance of 0.05, a power or 80%, and supposing equally sized samples (36 residents as in our 2015 baseline study), then the minimum detectable effect size will be 20 minutes, which corresponds to a reduction of just over 20% of the time dedicated to administrative tasks. Calculations were performed using the power twomeans command of stata and recalculating the standard deviation from the standard error.

ABSTRACT

2

Background: Due to an increasing number of complex polymorbid patients, a heavier administrative burden, and the evolution of young residents' expectations, organization of work in internal medicine wards is of outmost importance. In a 2015 study, we showed that residents spent 1.5 hours on administrative tasks and 1.7 hours with patients per day. In addition, residents switched activity on average 15 times per hour. This study motivated major reforms: task delegation to non-medical professionals, reorganization of the workday's schedule, and implementation of an early morning inter-professional decision meeting. An associated reduction in administrative and working hours and increased time with patients could greatly improve job satisfaction and attractiveness for internal medicine.

Aim: We aim to quantify the impact of the organizational and structural reforms implemented in our department between 2016 and 2017 on residents' administrative workload, continuity and adequacy of work, duration of shifts, and time spent with patients.

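### The stated 20-minute detectable difference does not follow from the printed standard error of 36 minutes, and the calculation leaves out clustering of shifts within residents

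*Protocol*

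**What the plan says.** Section 4.7.2 starts from the 2015 baseline: "Using an average time spent on administrative tasks (92 minutes per dayshift"). It adds "a standard error of 36 minutes, a one-sided test, a significance of 0.05, a power or 80" per cent and assumes "equally sized samples (either 36 doctors or 66 observations as in our 2015 baseline study), then the minimum detectable effect size will be 20 minutes". It names a standard two-sample means command and says the inputs were prepared by "recalculating the standard deviation from the standard error". No SD is printed.

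The synopsis (Statistical Considerations) repeats the calculation for 36 residents only, with the same conclusion: "the minimum detectable effect size will be 20 minutes, which corresponds to a reduction of just over 20% of the time dedicated to administrative tasks". The synopsis entry on number of participants says "this number will be sufficient and cost-effective to show a significant reduction of 20 % of administrative tasks", and the abstract repeats this, equating 20% with 20 minutes per shift.

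Section 4.7 plans mixed models with the participant as cluster, and states: "One-sided tests will be used and statistical significance will be considered for p<0.05". Section 4.7.2 plans 35 residents observed on two shifts each, up to 70 observations.

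**The concern.** The inputs, the method and the result are all printed, so the result can be checked, and it fails. A standard error of 36 minutes around a mean of 92, from 36 residents or 66 shifts, would mean an SD two to three times the mean. The word cannot be passed over as a simple slip for SD, because the text describes a step that converts one into the other.

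This paragraph is the only numerical support for the power of the primary comparison, and the synopsis and abstract both rely on it to call the sample sufficient. A reader cannot tell what variability was assumed, for which unit, or what difference the study can detect. The calculation is also for two independent samples, while the planned analysis has up to two correlated shifts per resident.

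**Working it through.** **Inputs.** Mean 92 minutes; variability 36 minutes, labelled a standard error; one-sided 0.05; 80% power; equal groups of 36 residents or 66 observations; stated result 20 minutes (all section 4.7.2). One-sided testing is confirmed in section 4.7.

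**Formula.** For two equal independent groups, detectable difference = SD × √(2/n) × (1.645 + 0.842), that is SD × √(2/n) × 2.4865. Results from the noncentral t distribution are given alongside.

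**1. The plan's calculation as printed.** SD = SE × √n.
- n=36: SD = 36 × 6 = 216. Difference = 216 × √(2/36) × 2.4865 = 126.6 minutes (t: 127.8).
- n=66: SD = 36 × √66 = 292.5. Difference = 292.5 × √(2/66) × 2.4865 = 126.6 minutes (t: 127.3).

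The two agree because n cancels: the difference is SE × √2 × 2.4865 whatever the group size. It is about 138% of the 92-minute mean (126.6/92). Power for 20 minutes would be about 10.5%. The stated 20 minutes is not reproduced.

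**2. Reading 36 as the SD.**
- n=36: 36 × √(2/36) × 2.4865 = 21.1 minutes (t: 21.3), about 23% of 92.
- n=66, treated as independent: 36 × √(2/66) × 2.4865 = 15.6 minutes (t: 15.7), about 17% of 92.

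Neither gives 20 minutes.

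**3. Working back from 20 minutes (noncentral t).**
- n=36 needs SD 33.8, so SE = 33.8/6 = 5.63.
- n=66 needs SD 46.0, so SE = 46.0/√66 = 5.66.

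A standard error of about 5.65 minutes would therefore give the stated result at both sizes. That figure appears nowhere in the protocol.

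**4. Effect of clustering, for illustration.** Assume SD 36 per shift, different residents in the two surveys, 66 shifts in 36 residents in 2015 (66/36 = 1.833 per resident) and 70 shifts in 35 residents in 2018. The ICC is an assumption; the protocol gives none.

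Variance of the difference = 36² × [(1 + ICC)/70 + (1 + 0.833 × ICC)/66]; detectable difference = 2.4865 × its square root.

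| Assumed ICC | Detectable difference (minutes) |
|---|---|
| 0 | 15.4 |
| 0.5 | 18.5 |
| 1 | 21.2 |

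On the same formula, 80% power holds for 18.4 minutes (20% of 92) up to an ICC of about 0.48, and for 20 minutes up to about 0.76.

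**The case against.** The best defence is that the result may be right and only the printed input wrong. Under the described SE-to-SD method, an SE near 5.65 minutes gives 20 minutes for both 36 doctors and 66 observations. This stands as a possibility, and it removes two inferences that a reader might draw. One is that a single figure cannot serve both sample sizes: it can, because n cancels under that method. The other is that 36 must be the SD: the documents do not establish this.

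A reader might also infer that power is below 80%. With SD 36 and n=36, power is about 76% for 20 minutes and 70% for 18.4 minutes (noncentral t: 75.5% and 69.2%). But those figures need either a second shift that adds no information or 36 being the SD of resident means, and the protocol states neither. With the planned clustered shifts, 80% power is kept over a wide range of ICC.

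Nor is 20 minutes against 18.4 minutes a separate error. The plan describes 20 minutes as just over 20% (20/92 = 21.7%), and the shorter statements are rounding.

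Finally, the calculation did not set the sample size: section 4.7.2 presents 35 residents as a sample of convenience, all eligible ward residents may take part, and the 2015 group is fixed. That limits the consequence. It does not make the printed inputs yield the printed result.

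**Conclusion.** The point holds as an error in the stated calculation. As printed, the inputs give a detectable difference of about 127 minutes, not 20. Reading 36 as an SD gives about 21 or about 15.6 minutes depending on the unit, again not 20. The protocol does not allow a choice between a mislabelled SD and a misprinted SE. Whichever applies, the clustering used in the planned analysis is missing from the calculation.

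The first result rests only on the protocol's own figures. The clustered illustration rests on an assumed SD of 36 per shift and an assumed ICC. The claim that the sample suffices for a 20% reduction is therefore unsupported as written, but not shown to be false.

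**What to change.** - Correct section 4.7.2, both synopsis entries (Number of Participants and Statistical Considerations) and the abstract together.
- State the actual 2015 standard error or SD, labelled as such, and its unit: resident or shift.
- Recompute the detectable difference for 36 residents and 66 shifts against 35 residents and up to 70 shifts, using the within-resident ICC estimated from the 2015 data, so that the calculation matches the mixed model in section 4.7.
- Keep the claim of sufficiency for a 20% reduction only if that calculation supports it; otherwise restate the detectable difference or the power.

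The cost is one recalculation from data already held and consistent rewording. No extra participants are needed, and the planned analysis and conduct do not change.
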